7.2 Secondary endpoints

The secondary endpoints are as follows:

- The primary endpoint is to describe the clinical course of SARS-CoV-2 infection in cancer patients. This will include duration and severity of clinical symptoms, supportive treatments given, cancer treatments received and outcome of SARS-CoV-2 infection. (Arm A)
- Proportion of patients, at each sample timepoint, with SARS-CoV-2 viral clearance by throat/nose swab by RT-PCR. (Arm A)
- Time from start of symptoms to Day 0 testing in the study. (Arm A)
- Feasibility of SARS-CoV-2 antigen testing with a throat/nose or saliva lateral flow assay (Arm A) will be assessed by the following

- 1) Proportion of samples successfully collected, processed and result obtained
- 2) Proportion of samples with a positive result by lateral flow by the gold standard (throat/nose RT-PCR)

If both of these are greater than 80% then the test would be considered successful and further research worthwhile.

- Feasibility of SARS-CoV-2 antibody testing with a rapid lateral flow assay will be assessed by the following (Arms A&B)
 - 1) Proportion of samples successfully collected, processed and result obtained
 - 2) Proportion of samples with a positive result by lateral flow by the gold standard (laboratory serology)

If both of these are greater than 80% then the test would be considered successful and further research worthwhile.

7.3 Exploratory endpoints:

The following endpoints and analyses are planned to be performed:

- Investigate antigen dynamics over time to compare with quantitative RT-PCR (Arm A)
- To examine HLA-KIR interactions that shape CD8 anti-viral responses (Arms A & B)
- To explore the relationship between host immune genotype (e.g. HLA-KIR) and peripheral blood (Arms A & B) immune cell phenotype with viral clearance (Arms A & B)
- To investigate blood immune cell activation and transcriptome in participants (Arms A & B)

As the pandemic evolves, the priority of these exploratory endpoints are subject to change. Any other exploratory analyses not specified in this protocol will be ratified by the TMG prior to analysis.

8. Inclusion/Exclusion Criteria

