11.2 Specimen collection

The schedule of visits and specimen collection for Arm A and B is outlined in Tables 2 and 3 respectively. Each study visit has a window period to allow for flexibility of visits due to logistics and bank holidays. Refer to the lab manual for full details regarding the specimen collection and handling.

Throat/nose swabs

Throat/nose swabs will initially be collected at baseline (D0) as part of the diagnostic workup for SARS-CoV-2 infection. Subsequent throat/nose swabs will be taken at D7 (if an inpatient), D14, D28, D42 and D56. Two samples will be taken, one for standard of care testing and one for lateral flow assay and storage for further analysis later such as quantitative PCR.

Saliva

Saliva will be collected at each study visit, by asking the participant to provide a small amount of saliva (approximately 0.5mL) will be collected. Saliva will be tested by the lateral flow assay when available and excess material stored.

Blood

Approximately 30mL of blood will be taken at each study visit (Table 1).

Table 1 Blood specimens to be collected in CARDS study

Sample type	Key analyte
Serum (SST)	SARS-CoV-2 antibody testing ie IgG, IgM
Whole blood (EDTA)	Immune profiling

As the assays are currently under investigation, results of the research assays (i.e. LFA, IgG/IgM serology) will not be made known to clinical teams.

Table 2. Schedule of assessments (Arm A)

Assessment	D0	SARS-CoV-2 swab result check*	D7 ^a +/- 3 days	D14 +/- 3 days	D28 +/- 3 days	D42 +/- 3 days	D56 +/- 3 days
Informed consent	X						
Registration	X						
Patient demographics	X						
Medical history ^b	X						
Concomitant medications	X		X	X	X	X	X
Symptom assessment	X		X	X	X	X	X
Vital signs ^c	X		X	X	X	X	X
Haematology ^d	X		X	X	X	X	X
Biochemistry ^d	X		X	X	X	X	X
Imaging assessment ^d	X		X	X	X	X	X
Throat/nose swab ^e	X		X	X	X	X	X
Blood (serum and EDTA whole blood) ^f	X		X	X	X	X	X
Saliva ^g	X		X	X	X	X	X

Schedule of Assessments Table Key

* Not applicable if patients have tested positive for SARS-CoV-2 prior to D0. If negative and has a low clinical suspicion of SARS-CoV-2 infection, the patient will be removed from the study.

a: Only if an inpatient. D7 visit will be omitted for patients in the outpatient setting.

b: Includes past medical history, oncological history

c: Includes temperature, blood pressure, heart rate, respiratory rate, oxygen saturations by pulse oximetry.

d: Results only to be recorded in CRF if performed as part of clinical management.

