12.5 Study duration

The study is expected to take up to 6-9 months to complete accrual. If the recruitment target is reached before the predicted end date, then the trial will close early to any further recruitment. Conversely, if the target recruitment is not achieved by the estimated end date, the trial recruitment

period may be extended until the target number of patients is achieved depending on the overall status of the SARS-CoV-2 pandemic.

Individual participants whose throat/nose swab RT-PCR does not confirm SARS-CoV-2 infection and do not have a high clinical suspicion of SARS-CoV-2 infection at D0 will come off study at this time and no further clinical data or samples will be collected. Research samples will be destroyed. This only applies to Arm A.

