14.1 Sample size

Arm A

Based upon the current SARS-CoV-2 infection rates at the Royal Marsden NHS Foundation Trust, up to 60 patients (up to 50 patients with solid tumour or 10 with lymphoma) with confirmed SARS-CoV-2 infection by RT-PCR could be recruited in 6-9 months, assuming uptake of 40% (As per positivity rates in April 2020) in screening 150 patients.

For the primary endpoint, seroconversion, and the RT-PCR and LFA viral clearance secondary endpoints:

Arm A - Up to 60 SARS-CoV-2 positive patients are expected to be recruited in the study; the proportion of patients can be estimated with a 95% CI with a width of ±12.7%. In the 50 patient solid tumour cohort then this will be estimated with a 95% CI with a width of ±13.9%.

To account for lower recruitment rate of SARS-CoV-2 positive patients, the following table presents the maximum width of the 95% C.I.s, given a 50% observed proportion for the primary endpoint, according to different sample sizes (N).

An observed proportion of 50% has been selected, which is conservative and gives the widest possible 95% CI. (Table 4)

Table 4:

N	Proportion of patients, with a positive detection of IgM and IgG specific antibodies to SARS-CoV-2.	With of 95% CI
10	50%	± 31.0%
20	50%	± 21.9%
30	50%	± 17.9%
50	50%	± 13.9%
60	50%	± 12.7%

Arm B

For the primary endpoint up to 150 patients are expected to be recruited in Arm B. Considering a 10% antibody positivity rate [10], the proportion of patients can be estimated with a 95% CI with a width of ± 4.8%.

The clinical course of SARS-CoV-2 infection secondary endpoint is descriptive so no power calculation is required.

Due to the dynamic changes in the prevalence of SARS-CoV-2 infection during the pandemic, the study may be halted prematurely.

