14.2 Analysis plan

The primary endpoint will be presented as the proportion of patients at each sample time-point with 95% confidence interval Arms A and B will be reported separately.

Continuous data will be summarised as n, mean, standard deviation, median, minimum value and maximum value. Categorical data will be presented as frequencies and percentages.

Arm A:

The secondary endpoint, viral clearance, will be presented as the proportion of patients at each sample time-point with 95% confidence interval.

The clinical course of SARS-CoV-2 infection described as patient characteristics, and cancer diagnosis, will be summarised, as well as duration and severity of clinical symptoms, supportive treatments given, cancer treatments received and outcome of SARS-CoV-2 infection.

Feasibility of SARS-CoV-2 antigen testing with a lateral flow assay will be assessed by the following

- 1 Proportion of samples successfully processed and result obtained, with 95% confidence interval
- 2 Proportion of samples processed with a positive result by lateral flow, by the gold standard (throat/nose RT-PCR)

Arm B:

Feasibility of SARS-CoV-2 antibody testing with a lateral flow assay will be assessed by the following

- 1 Proportion of samples successfully processed and result obtained, with 95% confidence interval
- 2 Proportion of samples processed with a positive result by lateral flow, by the gold standard (SARS-CoV-2 laboratory serology test)

The formal statistical analysis plan will be developed based on the size of the available cohort and the performance of the experiment assays. The analysis will be developed in a separate molecular and statistical analysis plan which will be drafted and approved by the Trial Management Group (TMG) with statistical input. However, the above gives a guide as to the planned analyses.

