RT-PCR	Reverse Transcription-Polymerase Chain Reaction
SAP	Statistical Analysis Plan
SARS	Severe acute respiratory syndrome
SD	Standard deviation
SUSAR	Suspected unexpected serious adverse reaction
TMG	Trial management group

Amendment history

Date	Version	Timing in relation to analysis	Brief description of change	Justification for change
09.12.2021	1.0	First version prior to the final analysis	N/A	N/A

1. Study Summary

CARDS is an observational study which will investigate how host cancer status and immune phenotype links to SARS-CoV-2 infection clinical presentation, seroconversion, and viral clearance. The study will also evaluate rapid antigen/antibody lateral flow tests.

2. Study objectives

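### Does the 80% success rule for the antibody lateral flow test need a criterion for serology-negative samples?

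*Protocol*

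**What the plan says.** Protocol 7.2 lists feasibility of the antibody lateral flow test as a secondary endpoint for Arms A and B. Item 1 is the share of samples that are collected, processed and give a result. Item 2 is "Proportion of samples with a positive result by lateral flow by the gold standard (laboratory serology". The decision rule is "If both of these are greater than 80% then the test would be considered successful and further research worthwhile".

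Protocol 14.2 repeats the endpoint under Arm B, with item 2 as "Proportion of samples processed with a positive result by lateral flow, by the gold standard (SARS-CoV-2 laboratory serology test". It does not repeat the 80% threshold. It leaves the formal analysis to a separate plan and adds "However, the above gives a guide as to the planned analyses".

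The SAP, signed in December 2021, is that plan. Section 6 says Arm A is not analysed because one patient was recruited. Section 6.2 sets out the secondary endpoints as IgG positivity, neutralisation and antibody fold rises; lateral flow is absent. Section 11 lists the departures from the protocol. Item 3 says neutralisation results take the place of lateral flow in the sensitivity and specificity analyses, and item 5 drops the exploratory endpoints. Section 1 still states "The study will also evaluate rapid antigen/antibody lateral flow tests", and sections 2.2 and 3.1 carry similar text.

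**The concern.** A rule that declares a diagnostic test successful should penalise false positives, and this one has no specificity or negative-agreement item. Arm B enrols people without symptoms, so at the planning rate about nine samples in ten are antibody-negative. That is where false positives of an antibody test would show. Item 2 can also be read in three ways, and the reading can reverse the verdict on the same data.

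The SAP does not settle the reading, and nowhere mentions the feasibility endpoint or the 80% rule. A reader could fear that a poor test will be called successful, or that a prespecified secondary endpoint has disappeared without explanation.

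**Working it through.** **Inputs.** Arm B has up to 150 patients (Protocol 14.1). The planning rate is "Considering a 10% antibody positivity rate" (same section). The threshold is strictly above 80% (Protocol 7.2). The sensitivity (Se) and specificity (Sp) values below are assumptions, because the documents give none.

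**The plan's own figure.** The Arm B half-width is 1.96 × √(0.10 × 0.90 / 150) = 4.8%, as stated in 14.1. It concerns antibody prevalence; no sample size or error rate is given for the 80% rule.

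**Three readings of item 2.** With prevalence π = 0.10, 150 samples at one visit contain 150 × 0.10 = 15 positives and 135 negatives.

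- Positive agreement, among serology-positives: Se
- Share of all processed samples: π·Se + (1 − π)(1 − Sp)
- Positive predictive value (PPV), among lateral-flow-positives: π·Se / [π·Se + (1 − π)(1 − Sp)]

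| Test (Se/Sp) | Positive agreement | Share of samples | PPV |
|---|---|---|---|
| Perfect (100/100) | 100% | 10% | 100% |
| Always positive (100/0) | 100% | 100% | 10% |
| 90/50 | 90% | 54% | 16.7% |
| 90/95 | 90% | 13.5% | 66.7% |
| 90/98 | 90% | 10.8% | 83.3% |

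The always-positive test passes on the first two readings and fails on the third. The share reading fails a perfect test, so it cannot be the intended one. The PPV reading does penalise false positives. No reading gives credit for a correct negative.

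**Effect of a negative-agreement criterion, positive-agreement reading, one visit.** Exceeding 80% needs 13 of 15, since 12/15 is exactly 80%. P(X ≥ 13 | n = 15, p = 0.90) = 0.816 whatever the specificity. Exceeding 80% of 135 needs 109, since 108/135 is exactly 80%. P(X ≥ 109 | n = 135) is about 0 at Sp 50% and 0.9996 at Sp 90%. The joint pass probability is therefore about 0 for the 90/50 test and 0.816 × 0.9996 = 0.816 for the 90/90 test. The criterion would separate the two tests if it were used.

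These figures rest on one visit at 10% positivity. Four visits at a constant 10% would give about 60 positives and a cut-off of 49/60, with pass probabilities of 0.449 at Se 80% and 0.985 at Se 90%. That treats repeat samples as independent, which they are not. Actual positivity is unknown because the SAP includes patients vaccinated before Day 0. At 20%, 50% and 80% positivity the split would be 30/120, 75/75 and 120/30.

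**Where the rule would be applied.** Tracing it through the SAP:

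1. Antigen test, Arm A: not analysed (SAP 6; section 11 item 1).
2. Antibody test, Arm A: not analysed, for the same reason.
3. Antibody test, Arm B: absent from the secondary endpoints in 6.2 and from the methods in 7.2.
4. Sensitivity and specificity, Arm B: spike IgG against neutralisation (6.3.1 and 7.3.1). Specificity is computed among neutralisation-negatives, so reference negatives are scored here.

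The number of lateral flow results in the planned analysis is zero. A new criterion in the rule has nothing to act on.

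**The case for a change.** The strongest reply is that section 11 item 3 covers only the accuracy analyses. Feasibility is a secondary endpoint with its own success claim, and its completion item has no counterpart in a neutralisation assay. Item 5 withdraws the exploratory endpoints only. The substitution is also not like for like: in the protocol lateral flow is the test under study and serology the reference, whereas in the SAP spike IgG is the test and neutralisation the reference. With SAP 1, 2.2 and 3.1 still promising lateral flow work, a reader cannot say for certain whether the endpoint was withdrawn or left unreported, and one sentence would settle it.

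All of that is accurate, and it stands as a remark on documentation. It does not show that any planned estimate, interval or conclusion would differ. The operative lists are SAP 6.2 and 7.2, and section 11 tells the reader that lateral flow results gave way to neutralisation. The protocol described its own analysis text as a guide, so the SAP was entitled to replace it.

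Nor is the gain clear if a lateral flow result were reported after all. An 80% negative-agreement threshold has no source in the documents. A 90/81 test would meet both thresholds in expectation, yet at 10% positivity its PPV is 0.09 / (0.09 + 0.171), about 34%. Positive agreement would rest on about 15 samples, and 13/15 has an exact 95% interval of 59.5% to 98.3%. In Arm A the criterion could not have been checked in PCR-negative, low-suspicion patients: "Research samples will be destroyed. This only applies to Arm A".

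**Conclusion.** The observation about the rule is right: item 2 is ambiguous and no reading credits a correct negative. It calls for no change, because the SAP as written produces no lateral flow result and makes no success claim. The effect on the planned analysis is nil.

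The residue is clerical. The feasibility endpoint and its 80% rule lapse without being named, and three SAP sections retain carried-over wording. Section 11 item 3, read with 6.2, lets a careful reader see what happened. The stakes would be low in any case: the rule leads only to a view on further research, and "results of the research assays (i.e. LFA, IgG/IgM serology) will not be made known to clinical teams".

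This rests on one assumption, that the report follows the SAP. If a lateral flow result were reported none the less, a competent analyst would show the full two-by-two table against a named serology, with exact intervals for positive and negative agreement, and would not lean on the 80% rule.

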8.1 Number of patients

Arm A: Up to 60 patients with solid tumour malignancy or lymphoma with confirmed diagnosis of SARS-CoV-2 by RT-PCR will be recruited over the study period.

Arm B: Up to 150 patients with solid tumour malignancy or lymphoma with no clinical suspicion of COVID-19

Patients will be recruited from the Royal Marsden NHS Foundation Trust in both the inpatient and outpatient setting.

8.2 Inclusion criteria

1) Suspected COVID-19 infection undergoing diagnostic testing by SARS-CoV-2 RT-PCR or within 14 days of confirmed COVID-19 infection by SARS-CoV-2 RT-PCR (Arm A)

OR

No symptoms of SARS-CoV-2 infection (Arm B)

2) Metastatic or advanced solid organ malignancy, including lymphoma

OR

Early stage solid organ malignancy having received or planning to commence radiotherapy, chemotherapy or targeted agents

3) Patient is \geq 18 years of age.

4) Patient can understand the patient information sheet and is able to provide written informed consent.

8.3 Exclusion criteria

There are no exclusion criteria for this study.

8.4 Subject withdrawal criteria

Patients have the right to withdraw fully or partially from the study at any time and for any reason without prejudice to his or her future medical care by the physician at the institution. Patients who are withdrawn from the study will be replaced.

Reasons for removal of patients from the study may include:

- withdrawal of consent (see above)
- administrative decision by the Investigator, Chief Investigator or Sponsor
- ineligibility
- patient non-compliance

Patients enrolled to the study who have tested negative for SARS-CoV-2 by RT-PCR and have a low clinical suspicion of COVID-19 will be withdrawn. No further follow-up will be conducted. Patients who have previously provided written consent who have previously tested negative for SARS-CoV-2

can have the D0 assessments repeated if there are new symptoms suggestive of SARS-CoV-2 infection.

9. Methodology

9.1 Informed consent

All patients will be consented by any health care professional with GCP training who has been delegated by the Principal investigator can obtain consent from eligible patients. All staff taking consent will have received training and be approved as competent in taking consent for this study by the chief investigator.

9.2 SARS-CoV-2 infection confirmation (Arm A)

Following a baseline throat/nose swab, if SARS-CoV-2 infection is confirmed, clinical data and additional samples are collected at the study time-points outlined in section 11. If SARS-CoV-2 infection is negative and deemed by the Investigator to have low clinical suspicion of SARS-CoV-2 infection no further samples or data will be collected and the patient will come off study. In the case the SARS-CoV-2 throat/nose swab is equivocal, the patient will remain on study and repeat testing will be performed as per local standard (Figure 1, Table 2). If a patient has a negative swab result but deemed by the Investigator to have a high clinical suspicion of SARS-CoV-2 infection, then the patient will remain on study. Patients who are within 14 days of a positive for SARS-CoV-2 by RT-PCR are eligible for entry into Arm A and the initial visit will be designated D0.

9.3 Asymptomatic patients with no clinical suspicion of COVID-19 (Arm B)

[figure not shown]
Patients with no current symptoms of COVID-19 will be eligible for inclusion in Arm B. Following written consent, samples (blood) will be collected from patients. Blood will be collected from patients on Day 0, 28, 56 and 84 (Figure 1, Table 3). Attempts will be made to ensure these blood collections will coincide with standard of care hospital visits.

Patients enrolled in Arm B develop COVID-19 symptoms or have confirmed COVID-19 can be invited to participate in Arm A. Patients will have to provide written consent for Arm A.

9.4 Personal protective equipment (PPE)

All staff performing study assessments including informed consent will require adequate personal protective equipment and adherence to infection control guidelines as per hospital guidance.

Figure 1 study schema (Arms A and B):

10. Data acquisition

Clinical data including demographics, medical history, medications, vital signs and symptom assessment will be collected as described in the schedule of assessments at the time of study visits. Additional information will be supplemented from the electronic patient records as appropriate. Standard investigations such as haematology, biochemistry and imaging assessments will only be performed if indicated by the treating unit. Results of such investigations will be recorded in the CRF.

11. Data analysis

11.1 Baseline assessments

Following initial eligibility checks and informed consent, the following baseline data will be collected.

For Arm A and B:

- Patient demographics
- Medical history (including history of malignancy and treatment)
- Concomitant medications
- SARS-CoV-2 symptom assessment

For Arm A only:

- Vital signsHaematology, biochemistry and imaging results (if performed as part of clinical management)

11.2 Specimen collection

The schedule of visits and specimen collection for Arm A and B is outlined in Tables 2 and 3 respectively. Each study visit has a window period to allow for flexibility of visits due to logistics and bank holidays. Refer to the lab manual for full details regarding the specimen collection and handling.

Throat/nose swabs

Throat/nose swabs will initially be collected at baseline (D0) as part of the diagnostic workup for SARS-CoV-2 infection. Subsequent throat/nose swabs will be taken at D7 (if an inpatient), D14, D28, D42 and D56. Two samples will be taken, one for standard of care testing and one for lateral flow assay and storage for further analysis later such as quantitative PCR.

Saliva

Saliva will be collected at each study visit, by asking the participant to provide a small amount of saliva (approximately 0.5mL) will be collected. Saliva will be tested by the lateral flow assay when available and excess material stored.

Blood

Approximately 30mL of blood will be taken at each study visit (Table 1).

Table 1 Blood specimens to be collected in CARDS study

Sample type	Key analyte
Serum (SST)	SARS-CoV-2 antibody testing ie IgG, IgM
Whole blood (EDTA)	Immune profiling

As the assays are currently under investigation, results of the research assays (i.e. LFA, IgG/IgM serology) will not be made known to clinical teams.

Table 2. Schedule of assessments (Arm A)

Assessment	D0	SARS-CoV-2 swab result check*	D7 ^a +/- 3 days	D14 +/- 3 days	D28 +/- 3 days	D42 +/- 3 days	D56 +/- 3 days
Informed consent	X						
Registration	X						
Patient demographics	X						
Medical history ^b	X						
Concomitant medications	X		X	X	X	X	X
Symptom assessment	X		X	X	X	X	X
Vital signs ^c	X		X	X	X	X	X
Haematology ^d	X		X	X	X	X	X
Biochemistry ^d	X		X	X	X	X	X
Imaging assessment ^d	X		X	X	X	X	X
Throat/nose swab ^e	X		X	X	X	X	X
Blood (serum and EDTA whole blood) ^f	X		X	X	X	X	X
Saliva ^g	X		X	X	X	X	X

Schedule of Assessments Table Key

* Not applicable if patients have tested positive for SARS-CoV-2 prior to D0. If negative and has a low clinical suspicion of SARS-CoV-2 infection, the patient will be removed from the study.

a: Only if an inpatient. D7 visit will be omitted for patients in the outpatient setting.

b: Includes past medical history, oncological history

c: Includes temperature, blood pressure, heart rate, respiratory rate, oxygen saturations by pulse oximetry.

d: Results only to be recorded in CRF if performed as part of clinical management.

e: Two samples will be taken, one for diagnostic testing and one for research purposes and storage for further analysis.

f: For collection of serum and whole blood. See laboratory manual for full details

g: See laboratory manual for collection details.

Arm B:

Blood

Approximately 30mL of blood will be taken at each study visit (D0, D28, D56, D84). The blood samples taken are outlined in Table 3.

Table 3. Schedule of assessments (Arm B)

Assessment	D0	D28 +/- 10 days	D56 +/- 10 days	D84 +/- 10 days
Informed consent	X			
Registration	X			
Patient demographics	X			
Medical history ^a	X			
Concomitant medications	X			
Symptom assessment ^b	X	X	X	X
Blood (serum and EDTA whole blood) ^b	X	X	X	X

Schedule of Assessments Table Key

a: Includes past medical history, oncological history

b: See laboratory manual for full details

12. Study Organisation/ Trial Monitoring and Management Strategy

